9.2.6 Recording Adverse Events

As quality and precision of acquired AE data is of key importance, the Investigator should use the AE definitions provided in above sections and observe the following guidelines when completing the AE pages of the eCRF:

- Whenever possible, recognized medical terms should be used to describe AEs rather than colloquialisms (for example, 'influenza' rather than 'flu'), and abbreviations should be avoided.
- AEs should be described using a specific clinical diagnosis rather than component signs or symptoms, if this is available (for example, 'congestive heart failure' rather than 'dyspnea, rales and cyanosis'). However, signs and symptoms considered unrelated to an identified disease or syndrome should be reported as individual AEs in the eCRF.
- AEs occurring secondary to other events (e.g., sequelae or complications) should be identified by the primary cause. A primary AE, if clearly identifiable, generally represents the most accurate clinical term to record in the AE pages of the eCRF.

Additional guidance can be found in the eCRF completion conventions provided by the Sponsor.

An Adverse Event (AE) is any untoward medical occurrence in a study subject which is temporally associated with the use of a medicinal product or study conduct, regardless of its potential relationship to the medicinal product or study conduct. An AE, therefore, can be any unfavorable or unintended sign, including any abnormal laboratory finding, symptom, or disease (new or exacerbated), whether or not related to the IMP or study

Protocol VTX-801_CLN_001	Investigational Product: VTX-801
	Version: 9 dated 07 AUG 2023
	Author: Aixial Group CRO

conduct. AEs should be followed-up in accordance with the procedures described in Section 9.2.7.

AEs will be captured differently in the eCRF depending on the date of onset and causality assessment (per Investigator's judgment) as described below:

Table 16 Capture of Adverse Events in the eCRF

AE onset date	Types of AEs to be captured in the eCRF
From signing the ICF, including Screening 1 and until start of Screening 2	
 Only AEs considered to be possibly, probably or definitely related to the study procedures
From Screening 2 included until 1-year post VTX-801 infusion visit included	
 All AEs

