After the 1-year post infusion visit until completion of the 5-year follow-up visit included	
 All AEs except those AEs incontrovertibly unrelated to VTX-801, radiocopper and study procedures
After the 5-year follow up period	
 Only SAEs considered to be possibly, probably or definitely related to VTX-801

Abbreviations: AE= Adverse Event; eCRF= electronic Case Report Form; ICF= Informed Consent form; SAE= Serious Adverse Event.

Note: The above table refers to newly onset AEs. *Follow-up* details regarding the AEs previously entered into the eCRF will be captured regardless of the type of AE. (Refer to Section 9.2.7).

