9.3 Serious Adverse Events

9.3.1 Definition of Serious Adverse Event

A SAE is defined as an AE which meets one of the following criteria:

- Results in death.
- Is life-threatening (defined as a patient at immediate risk of death at the time of the event).
- An event requiring inpatient hospitalization or prolongation of existing hospitalization.

Note: In general, hospitalization signifies that a person has been detained (usually overnight) at a hospital or emergency ward for observation and/or treatment. Emergency room visits which do not result in admission to the hospital should be evaluated for one of the other serious outcomes (e.g., life-threatening; required intervention to prevent permanent impairment or damage; other serious, medically important event).

- Results in a persistent or significant disability/incapacity.

Protocol VTX-801_CLN_001	Investigational Product: VTX-801
	Version: 9 dated 07 AUG 2023
	Author: Aixial Group CRO

Note: The term significant disability/incapacity means a substantial disruption of a person's ability to conduct normal life functions, i.e., the AE resulted in a significant, persistent or permanent change, impairment, damage or disruption in the patient's body function/structure, physical activities and/or quality of life.

- Is a congenital anomaly or birth defect in the case of pregnancy.
- Any other important medical event that may not result in death, be life threatening, or require hospitalization, may be considered a serious adverse experience when, based upon appropriate medical judgment, the event may jeopardize the patient and may require medical or surgical intervention to prevent one of the outcomes listed above. Examples of such medical events include allergic bronchospasm requiring intensive treatment in an emergency room or at home, blood dyscrasias or convulsions that do not result in inpatient hospitalization, or the development of drug dependency or drug abuse.

It is important to distinguish between serious and severe AEs. Severity is a measure of intensity whereas seriousness is defined by the above criteria. An AE of severe intensity might not necessarily be considered serious. For example, persistent nausea for several hours may be considered severe, but not a SAE. Conversely, a stroke resulting in only a limited degree of disability may be considered mild, but would be a SAE.

SAEs will be:

- Recorded in the eCRF if the criteria described in Section [9.2.6 \(Table 15\)](#) are met.

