9.3.2 Reporting of Serious Adverse Events and Adverse Events of Special Interest

Any SAE meeting the criteria described in Section [9.2.6 \(Table 15\)](#), any AESI meeting the definitions in Section [9.6](#), or any event applicable to the study Stopping Rules must be **entered into the eCRF within 24 hours of first awareness** of the event by study personnel. A causality assessment must be provided at the time of reporting and a

Protocol VTX-801_CLN_001	Investigational Product: VTX-801
	Version: 9 dated 07 AUG 2023
	Author: Aixial Group CRO

narrative should also be provided. Any SAEs experienced after the 5-Year follow up period should be reported to the designated CRO designee safety group if the Investigator has assessed that the SAE is possibly, probably or definitely related to IMP administration.

Entry of an SAE/AESI (or updated SAE/AESI information) into the eCRF will trigger an automatic alert to the designated CRO Safety group (Aixial).

If the EDC system is **not available**, SAEs/AESIs should be reported by emailing or faxing a completed paper SAE/AESI Report Form to the designated CRO safety group within 24 hours of site awareness. The SAE/AESI may be reported by telephone; however, this must be followed up within 24 hours with either a completed paper SAE/AESI Report Form (if EDC system is still not available) or by recording it into the eCRF (if EDC becomes available in the meantime). Additionally, it may be necessary for the designated CRO safety group to communicate with the Investigator if additional information is required. Note: when EDC becomes available, the SAE/AESI Report must still be entered in the eCRF despite the paper SAE Form being submitted.

During both business and non-business hours, the email address, telephone and fax numbers listed below can be used to notify the designated CRO safety group. If a paper SAE/AESI Report Form is submitted via email or fax and no acknowledgement is received within one working day, the report should be re-submitted.

Reportable Events Hotline:
Aixial Group CRO (formerly Cmed)
Email: [REDACTED] [REDACTED] [REDACTED] [REDACTED] [REDACTED]

All additional follow-up evaluations must be reported within 24 hours of site awareness, following the same processes. The Sponsor is responsible for complying with applicable regulatory reporting requirements for SAEs and, where necessary, for ensuring the relevant authorities are notified (see Section 9.4). The Investigator will ensure the

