9.4 Regulatory Reporting of Safety Events

Following notification from the Investigator, the Sponsor and/or its designee (CRO) will report adverse events which are both serious and unexpected (not previously described in the reference safety information in the approved IB) and that are possibly, probably or definitely related with the IMP (otherwise known as SUSARs) to the FDA, EMA, other concerned Regulatory Authorities, IRB/IECs and Investigators within the required timelines as specified in 21 CFR Part 312.32, EU Directive 2001/20/EC, the European Commission's "Detailed guidance on the collection, verification, and presentation of adverse event/reaction reports arising from clinical trials on medicinal products for human use" (CT-3, June 2011), ICH GCP Guidelines and other applicable national regulatory requirements. Typically, fatal and life-threatening SUSARs must be reported within 7 calendar days and all other SUSARs must be reported within 15 calendar days. All SAEs designated as not related to the IMP, will be reported to the concerned Regulatory Authorities, and IRB/IECs at least annually in a summary format.

Additionally, adverse events may occur during a clinical trial which do not fall within the definition of a SUSAR and thus are not subject to the reporting requirements for SUSARs, even though they may be relevant in terms of patient safety. Examples are new adverse events related to the conduct of a trial or the development of an IMP likely to affect the safety of patients such as:

- A SAE which could be related with the trial procedures and which could modify the conduct of the trial.
- A significant hazard to the patient population such as lack of efficacy of an IMP used for the treatment of a life-threatening disease.
- A major safety finding from a newly completed animal study (such as carcinogenicity).
- A temporary halt of a trial for safety reasons, e.g. in accordance with Stopping Rules (see Section 6.3); or if the trial is conducted with the same IMP in another country by the same Sponsor, recommendations of the DMC, if any, where relevant for the safety of patients.

Protocol VTX-801_CLN_001	Investigational Product: VTX-801
	Version: 9 dated 07 AUG 2023
	Author: Aixial Group CRO

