These adverse events/observations are not to be reported as SUSARs, but they might require other action, such as urgent safety measures and their notification, substantial amendments, or early termination of the trial, and shall be reported in accordance with applicable local regulations and guidelines.

In addition, the liver and neuropsychiatric serious TEAEs will be reported to the DMC (within 24 hours of awareness) and expeditiously adjudicated by the HAC in case of suspected DILI or by DMC in case of neuropsychiatric TEAE (if possible, within 48 hours). If the SAE is also unexpected, i.e., a SUSAR, this SAE must be timely reported to FDA and the other concerned Regulatory Authorities as per regulatory requirements (within 7 to 15 calendar days). The DMC will review all liver and neuropsychiatric TEAEs and provide supplemental causality assessment in addition to PI assessment and these assessments must be submitted to FDA for review. In addition, all TEAEs, irrespective of causality and grade, will be submitted in the Clinical Study Report.

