11.4.4.1 Adverse Events

AEs will be coded using the Medical Dictionary for Regulatory Activities (MedDRA). System Organ Class (SOC), High-Level Group Term (HLGT), High Level Term (HLT), Preferred Term (PT), and Lower-Level Term (LLT) will be attached to the clinical database.

AEs will be summarized based on the date of onset for the event. Summaries (number and percentage of patients) of treatment-emergent AEs will be provided by SOC and PT, by dose cohort and overall.

Treatment-emergent adverse event is defined as any AE that emerges during or after IMP administration having been absent pre-treatment or worsens relative to the pre-treatment state.

Events that are considered possibly, probably or definitely related to the IMP, deaths, SAEs, and AEs resulting in IMP discontinuation will also be tabulated by SOC and PT.

A tabulation will also be provided that summarizes at least treatment-emergent and treatment-related AEs (possibly, probably or definitely related) by maximum severity (i.e., CTCAE grade).

Duration of AEs will also be investigated as appropriate.

All AEs, including treatment-emergent and non-treatment-emergent AEs, will be listed in patient data listings.

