7.9.1 Adverse Events

Adverse events (AEs) will be coded using MedDRA dictionary.

AEs will be graded according to the National Cancer Institute – Common Terminology Criteria for Adverse Events (NCI-CTCAE) version 5, based on study protocol.

The following definitions will be used:

- Treatment-emergent AEs (TEAEs): AEs that occurred during on-treatment period, from the day of VTX-801 dosing,
- Related AEs: AEs suspected by the Investigator to have a relationship to study treatment (as recorded on the AE eCRF page, Relationship to VTX-801 = Possibly related, Probably related, Definitely related or missing,
- Serious Adverse Events (SAE): serious AEs (as recorded on the AE eCRF page, Does AE Meet the Definition of an SAE = Yes),
- AEs leading to Death: adverse event leading to death (as recorded on the AE eCRF page, Results in death, or Outcome = Fatal, or Grade = 5),
- Liver function AEs: adverse event meeting the definition of a suspected DILI (as recorded on the AE eCRF page, does AE meet the definition of a suspected DILI event? = Yes).

An overview summary table will present the number and percentage of patients with a TEAE, including:

- TEAEs / TEAEs related to study treatment,
- Serious TEAEs / Serious TEAEs related to study treatment,
- Liver TEAEs / Liver TEAEs related to study treatment,

- Adverse events of special interest (AESI) / AESI related to study treatment,
- Dose Limiting Toxicity / Dose Limiting Toxicity related to study treatment,
- TEAEs leading to death / TEAEs related to study treatment leading to death,
- TEAEs with NCI-CTCAE grade ≥ 3 / TEAEs related to study treatment with NCI-CTCAE grade ≥ 3 ,
- TEAE meeting any stopping rule,
- TEAE Related to Radiocopper Administration,
- TEAE related to Other Study Procedure.

In addition, the following tables will be produced by SOC and PT:

- TEAEs / TEAEs related to study treatment,
- Serious TEAEs / Serious TEAEs related to study treatment,
- Liver TEAEs / Liver TEAEs related to study treatment,
- TEAEs and maximum CTCAE grade / TEAEs related to study treatment and maximum CTCAE grade,
- TEAEs leading to death / TEAEs related to study treatment leading to death,
- Non-serious TEAE.

A patient with multiple occurrences of an AE will be counted only once in the AE category. SOCs will be sorted by descending order of frequency for the overall group, PTs will be sorted by descending order of frequency for the overall group within each SOC.

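### After the 1-year visit the eCRF may omit serious adverse events judged incontrovertibly unrelated, although Protocol 9.4 requires unrelated SAEs and all TEAEs to be reported

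*Protocol*

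**What the plan says.** Protocol 9.2.6 states that "AEs will be captured differently in the eCRF depending on the date of onset and causality assessment". Its Table 16 asks for all AEs from Screening 2 up to and including the 1-year visit. After that visit, and up to the 5-year visit, the requirement becomes "All AEs except those AEs incontrovertibly unrelated to VTX-801, radiocopper and study procedures".

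The same table governs serious events. Protocol 9.3.1 says that SAEs are "Recorded in the eCRF if the criteria described in Section" 9.2.6 are met. Protocol 9.3.2 sets the 24-hour entry requirement for "Any SAE meeting the criteria described in Section" 9.2.6, and Protocol 12.4.2 repeats that condition. All three call it Table 15, but the capture table printed in 9.2.6 is Table 16.

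Protocol 9.4 has no such filter. It says: "All SAEs designated as not related to the IMP, will be reported to the concerned Regulatory Authorities, and IRB/IECs at least annually". It adds that "all TEAEs, irrespective of causality and grade, will be submitted in the Clinical Study Report".

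SAP 7.9.1 plans tables of "Serious TEAEs / Serious TEAEs related to study treatment", with the same pairing for TEAEs overall, and a table of non-serious TEAEs. It does not distinguish events by the capture rule in force at onset.

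**The concern.** The primary objective is safety for up to 5 years, in an open-label first-in-human study without a control arm. An all-causality count is useful there because it does not depend on one investigator's attribution of one event. If the investigator's judgement decides whether an event is recorded at all, the count has already been filtered. An unrecorded event cannot be re-judged later, for example when a similar event occurs in another patient.

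The filter also leaves no trace. Incontrovertibly unrelated is not one of the five causality categories in Protocol 9.2.3, so the database cannot show how often it was applied. A reader of the SAP tables would take the TEAE and serious TEAE rows as complete for the whole of follow-up.

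**Working it through.** The documents give no figure to reproduce. The check sets the rules side by side and then bounds the exposure.

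**1. Are later events TEAEs?** Yes. Protocol 11.4.4.1 defines a TEAE as "any AE that emerges during or after IMP administration having been absent pre-treatment", or one that worsens from the pre-treatment state, with no causality condition and no end date. SAP 7.9.1 counts from the day of dosing, also without a causality condition; it does not define when the on-treatment period ends.

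**2. Does the filter reach SAEs?** Yes. Table 16 has no exemption for them in that row, and Protocol 9.3.1, 9.3.2 and 12.4.2 all defer to it. By contrast, Protocol 9.2.7 says that all SAEs are followed to resolution or stabilisation.

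**3. Is there another route for an ordinary SAE?** None is described for Years 2 to 5. Under Protocol 9.3.2, eCRF entry triggers the alert to the safety group. Paper and telephone reports are for when the EDC system is down, and the event must still be entered afterwards.

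**4. Which events are kept anyway?** Protocol 9.3.2 separately requires entry of AESIs and stopping-rule events.
- Stopping rules (6.3) include any death, Grade 3-4 toxicity, new malignancy and copper deficiency.
- AESIs (9.6) are reportable regardless of causality. They include DILI, ALT at or above 1.5 times baseline, and neurological, psychiatric or behavioural AEs.
- Whether a Grade 3 or 4 event that is clearly unrelated counts as toxicity is not stated.

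The clear loss is therefore an incontrovertibly unrelated SAE outside these lists, such as a Grade 1-2 event leading to hospitalisation, together with ordinary non-serious AEs.

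**5. Which outputs are affected?** An event judged incontrovertibly unrelated would never enter a treatment-related row. Only the all-causality rows can be low.

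**6. Over what exposure?**
- Share of planned follow-up under the filter: (5 - 1) / 5 = 80%.
- Patients dosed: 4, with 2 in each of cohorts 1 and 2 (SAP 9).
- Ceiling: 4 patients x 4 years = 16 patient-years. SAP 3 describes a reduced safety follow-up and gives no length, so the actual figure is expected to be lower.

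**7. What can one missed event do?** Percentages use N as denominator (SAP 7.1), and a patient is counted once per category (SAP 7.9.1). If a patient's only SAE is missed, the serious TEAE percentage falls by 1/4 = 25 points overall and 1/2 = 50 points in that patient's cohort. If the patient has another serious TEAE, the overall row does not change.

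**The case against.** Lighter AE collection in long-term follow-up is a deliberate and common choice. The exclusion is also narrower than the Unrelated category: the event must be beyond dispute with respect to VTX-801, radiocopper and study procedures alike. Most of what Protocol 9.4 asks for can still be produced: all events up to the 1-year visit, later unrelated SAEs that are not incontrovertibly so, and all AESIs and stopping-rule events. The abbreviated CSR rests on an interim analysis held before 1 year after the last dosing, so much of its data falls under full capture. All of this stands and limits the size of the problem. It does not remove the conflict, because 9.4 makes no exception and no other entry route is described.

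Four stronger readings are tempting but not supported.
- **Deaths and other major events are lost.** They are not; Protocol 9.3.2 requires their entry separately.
- **The filter inflates the related share.** No ratio of related to total events is planned, and the related rows do not change.
- **A patient who terminates before Year 1 has no capture standard.** Either the all-AEs row continues to apply, or the early termination visit stands in for the 1-year visit, since Protocol 10.10 gives it that visit's content. Which of the two applies is unclear, but both give a standard.
- **A number of missing SAEs can be estimated.** The documents give neither a background SAE rate nor the share that would be judged incontrovertibly unrelated.

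**Conclusion.** The inconsistency is real and sits in current text. A site that follows Table 16 may leave some SAEs and ordinary AEs out of the eCRF after the 1-year visit, and Protocol 9.4 then cannot be met in full. The all-causality TEAE and serious TEAE rows may be too low for that period.

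The scale is limited. The effect falls mainly on the final analysis and CSR addendum, plus any post-Year-1 data of earlier-dosed patients in the interim analysis. Exposure is at most 16 patient-years, a ceiling that assumes all 4 dosed patients pass the 1-year visit and are followed to Year 5. The count lost is unknown and may be zero. The point still deserves correction because, with 4 patients, a single omission can shift the overall serious TEAE percentage by 25 points and would be invisible in the data. This conclusion assumes that the eCRF is the source of the AE tables, as SAP 7.9.1 indicates, and that no unseen site guidance already overrides Table 16.

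**What to change.** In the post-1-year row of Table 16, require all SAEs regardless of causality to the end of follow-up, and keep the incontrovertibly unrelated filter for non-serious AEs only. Align Protocol 9.3.1, 9.3.2 and 12.4.2 with that row and correct their table number. Reword the CSR sentence in 9.4 so that it allows for the non-serious AEs not collected after the 1-year visit.

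In SAP 7.9.1, either split the TEAE and non-serious TEAE tables by capture period, or footnote them to say that incontrovertibly unrelated non-serious AEs were not collected after the 1-year visit. Optionally, state whether an early termination visit before Year 1 (Protocol 10.10) counts as the 1-year visit for Table 16.

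The cost is a short amendment and a few extra SAE records from 4 patients, for whom Protocol 6.5 and 6.6 already call for contact at least every 6 months. If any of them has already passed the 1-year visit, the site should be asked about SAEs since then.

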9.2.7 Follow-up of Adverse Events

Follow-up of AEs is defined as follows:

- The AEs which occur after signing the ICF and up to completion of the 5-Year follow-up period after VTX-801 administration will be recorded in the AE pages of the eCRF per the criteria defined above.

Protocol VTX-801_CLN_001	Investigational Product: VTX-801
	Version: 9 dated 07 AUG 2023
	Author: Aixial Group CRO

- All AEs that were previously captured in the eCRF, and all SAEs, will be followed until resolution or until the Investigator assesses them as 'chronic' or 'stable'.
- If the Investigator becomes aware of a SAE, including death, after the 5-Year follow-up period and the SAE is considered by the Investigator to be possibly, probably or definitely related to the study product, it will be reported to the designated CRO safety group in accordance with Section 9.3.2.

Taking the above post-treatment safety surveillance reporting requirements into account, AE follow-up information data will be recorded in the AE pages of the eCRF up until Last Patient Last Visit.

After Last Patient Last Visit and 2 weeks prior to any data lock, the status of all outstanding ongoing AEs will be checked and any up-to-date change made in the eCRF. At that stage, as considered appropriate by the Sponsor, follow-up information will continue to be requested from the Investigator on specific AEs (and in any case all SAEs considered possibly, probably or definitely related to the study product by the Investigator) although related details will not be recorded in the eCRF beyond database lock.

